After 50% of all study subjects have presented for the 6-week post-operative check, the overall rate of mesh and suture exposure will be calculated. If this rate is >12%, the study will be terminated. A second stopping parameter will be a difference in erosion rates between the two groups of >50%.

Reporting Adverse Events

Adverse events will be recorded and reported according to criteria and timeline below. Sites will also follow local regulatory standards for AE reporting.

All AEs must be recorded on the AE CRF, entered into the site AE log, then entered into REDCap. An event number will be assigned by each site and recorded on the CRF according to the number of AEs reported per patient. Each site investigator will determine the relationship of the AE to the operative procedures, the relationship of the AE to the pelvic floor, and the severity of each reportable AE.

SAEs must be reported to the DSMB within two business days as outlined above in the Data Safety Monitoring Board section.

Reportable AEs include those determined to be related to the operative procedures or pelvic floor. AEs not related to the operative procedures or pelvic floor will not be collected. Operative procedures include the following: Hysterectomy, sacrocolpopexy, sling, anterior and posterior vaginal repairs.

Please note that underlying diseases are not reportable AEs unless there is an increase in severity or frequency during the course of the investigation. Death should not be recorded as an AE, but as an outcome of a specific SAE. If an AE has not resolved at the time of AE Form completion, save form as incomplete in REDCap until resolved. Once resolved, complete item 22 on AE form and enter into REDCap and save form as complete.

Adverse Event Definitions

Adverse Event: any untoward medical occurrence, unintended disease or injury, or any untoward clinical signs (including abnormal laboratory finding) in subjects, whether or not related to the operative procedures

Serious Adverse Event: an adverse event that:

- Led to death
- Led to serious deterioration in the health of the subject that either resulted in
 - a life-threatening illness or injury
 - a permanent impairment of a body structure or a body function
 - in-subject or prolonged hospitalization of existing hospitalization
 - medical or surgical intervention to prevent life-threatening illness or injury or permanent impairment to a body structure or a body function
- Led to fetal distress, fetal death or a congenital abnormality or birth defect

Relationship of AE to Operative Procedures

Unrelated: No evidence that the timing if the AE has a relationship to the operative procedures performed.

Possibly Related: The AE has a timely relationship to the operative procedures performed, however a potential alternative etiology may be responsible for the AE.

Probably Related: The AE has a timely relationship to the operative procedures performed and the causative relationship can clearly be established. No potential alternative etiology is apparent.

Relationship to Pelvic Floor

Unrelated: No evidence that the AE has a relationship to the pelvic floor and supporting tissues

Related: If any of the following are met

- The AE is determined to be potentially related to the pelvic floor and supporting tissues including but not limited to lacerations, avulsions, tears, pelvic organ prolapse (cystocele, rectocele, enterocele, uterine, rectal), urinary incontinence (stress, urge), urinary voiding dysfunction (retention, obstructed voiding, incomplete emptying), fecal incontinence (urgency, irritable bowel syndrome), defecatory dysfunction (constipation, obstipation, stool trapping, IBS), pain (dyspareunia, pelvic, perineal), and infection (bladder, urinary tract, vaginal)
- There is a strong relationship to the pelvic floor and supporting tissues, and another etiology is unlikely
- There is no other reasonable medical explanation for the event

Severity

Mild: Awareness of signs or symptoms, but easily tolerated and are of minor irritant type causing no loss of time from normal activities. Symptoms do not require therapy or a medical evaluation; signs and symptoms are transient.

Moderate: Events introduce a low level of inconvenience or concern to the participant and may interfere with daily activities, but are usually improved by simple therapeutic measures; moderate experiences may cause some interference with functioning.

Severe: Events interrupt the participant's normal daily activities and generally require systemic drug therapy or other treatment; they are usually incapacitating.

References

1. Wu JM, [name] CA, Conover MM, Pate V, Jonsson Funk M. Lifetime Risk of Stress Urinary Incontinence or Pelvic Organ Prolapse Surgery. *Obstet Gynecol*. May 6 2014.

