Please note that source data collected as part of routine clinical care may be used to complete CRFs as long as the window between prior data collection and operative procedures does not exceed six months. This includes previously performed POP-Q exams as well as previously collected questionnaires.

Randomization

Randomization will be assigned using RedCAP in the operating room *immediately prior* to mesh graft attachment to the vagina. Both types of sutures will be available at each site. Participants will be randomized to 2-0 GoreTex/CV4 GoreTex (depending on availability of Stitchkit) versus 2-0 PDS in blocks with block sizes of 2, 4 and 6 for each of the 5 sites. Randomization will be stratified by site.

Surgery (\leq 3 months from Baseline Visit)

Study data for the surgical procedures includes the Surgical Procedures Form and review of adverse events.

- Surgical Procedures Form
- Review of Adverse Events (if applicable)

Laparoscopic or Robotic Approach

Prior to sacral colpopexy all participants of the trial will undergo total laparoscopic hysterectomy (with or without robotic assistance) with or without bilateral salpingoophorectomy (at the discretion of the patient and surgeon).

Laparoscopic sacral colpopexy will be performed with or without robotic assistance. The configuration of the incisions is not standardized.

1. Total laparoscopic hysterectomy (with or without robotic assistance) will be performed in standard fashion and the uterus will be delivered through the vagina with no power morcellation performed. The vaginal cuff will be closed using an absorbable suture in 1 layer (suture type at the discretion of the operating surgeon). Closure of the vaginal cuff through a transvaginal approach is not allowed.
2. The same ultra-lightweight Type 1 polypropylene mesh (Upsylon, Boston Scientific) will be used for all study subjects.

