 - c) Assessment for re-intervention or re-surgery for recurrence or persistence of POP: No need for pessary use or additional surgical treatment for prolapse at any time after the initial procedure
 - d) No mesh / suture exposure
2. Assessment of participant changes in QoL, symptom bother, and sexual functioning at 1 year compared to baseline^{30,31}:
 - PFDI 20-Pelvic Floor Distress Inventory
 - PFIQ-7-Pelvic Floor Impact Questionnaire
 - PISQ-IR-Pelvic Organ Prolapse/Urinary Continence Sexual Questionnaire

3. Assessment of procedure-related or pelvic floor-related adverse outcomes in each group as classified according to the Clavien-Dindo surgical complication grading scale²⁹. Adverse events will be assessed intra-operatively, at 6 weeks, 6 months, and 1 year postoperatively.

STATISTICAL CONSIDERATIONS

Statistical Methods

Data analyses will include t-tests for continuous data, chi-square or Fisher's exact for categorical data, and multi-variable regression to assess the effects of any bivariate analyses found to have a positive relationship. Confidence intervals will be reported for continuous data and will be included in the assessment and reporting of outcomes. When the data are analyzed, both chi square and Fisher's exact analyses are performed and the appropriate test and associated p value will be used based on the proportion of samples with input less than 5% of the total population. Those with a small output will utilize Fisher's exact.

The data will be analyzed as Intent to Treat. Missing data may occur if subjects fail to return for follow up, thus we plan to over-recruit in order to account for a 20% drop-out rate. Since study participants are undergoing surgery, they are more likely to return for their follow-up visits since these are part of their standard post-operative care. This will decrease the rate of drop-outs. The fact that this is an RCT will minimize the chance of a differential drop-out rate between the groups.

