The rate of reported mesh exposure varies greatly from 0-27%, as discussed in our Background section on page 2 of the Investigator Protocol. Based on published data both at our institution and elsewhere in the literature, we determined that a 10% and 1% rate of mesh exposure in the two groups is both supported by data and clinically relevant, thus we are estimating a 9% difference in mesh erosion rates between the two groups: 1% vs 10%. This is a clinically significant difference that would affect a change in clinical practice.

Sample Size

The power calculation was performed using the statistical computation software Epi Info™ 7.1.3.10, developed on 3/11/14. It is a trademark of the Centers for Disease Control and Prevention and uses chi square for its computation of sample size for studies based on categorical data comparison such as the current study.

We are planning a study of independent cases and controls with 1 control(s) per case. Prior data indicate that the mesh exposure rate among controls is 10%. If the mesh exposure rate for experimental subjects is 1%, we will need to study 80 experimental subjects and 80 control subjects to be able to reject the null hypothesis that the failure rates for experimental and control subjects are equal with probability (power) 0.8. The Type I error probability associated with the test of this null hypothesis is 0.1. The alpha of 0.1 is based on a one-sided hypothesis, estimating that mesh exposure rates will be higher in the study arm using permanent suture compared to the study arm using absorbable suture. We will use an uncorrected chi-squared statistic to evaluate this null hypothesis. We plan to enroll a total 200 subjects across sites to account for up to 20% loss to follow up, thus the use of chi square is appropriate given the adequately large sample size.

We feel the sample size is appropriate based on our sample size calculation, taking into account the estimated rates of mesh exposure in the two groups, as well as our clinical judgment of the number of procedures that are performed each year at the study sites. In the past year each

study site has performed 50 cases, for a total of 200 cases at all combined sites. Therefore our sample size of 100 subjects per study arm is feasible for completion in the time allotted.

Primary Hypothesis

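### Randomisation is stratified by site but no named test uses site; if sites differ, the secondary comparisons are slightly conservative and give up a little power

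*Combined protocol and SAP*

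**What the plan says.** The Randomization section allocates participants "in blocks with block sizes of 2, 4 and 6 for each of the 5 sites" and adds that "Randomization will be stratified by site".

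Statistical Methods lists "t-tests for continuous data, chi-square or Fisher's exact for categorical data". Its only adjusted analysis is "multi-variable regression to assess the effects of any bivariate analyses found to have a positive relationship". No covariates are listed for that regression, and site is not mentioned.

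For the primary outcome, Sample Size says: "We will use an uncorrected chi-squared statistic to evaluate this null hypothesis". No stratified form is given.

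Secondary Hypotheses covers composite success, symptomatic success and adverse event incidence. It names no site-adjusted method, no alpha and no non-inferiority margin.

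**The concern.** Blocking within site forces the arms to be nearly balanced at each site, so differences between sites largely cancel out of the treatment comparison. A t-test or an unstratified chi-square still counts those differences as random error. Its standard error is then larger than the true variability of the estimate, the type I error falls below nominal, and some power is lost relative to an analysis that uses the strata.

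Site differences are plausible here. Robotic assistance is optional, incision configuration is not standardised, and the cuff suture, the sacral suture, peritoneal closure and several added procedures are left wholly or partly to the surgeon. The treating surgeon may also perform the follow-up POP-Q where nobody else at the site is qualified, and POP-Q feeds the composite.

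What is at stake is efficiency on the secondary outcomes. In addition, with no stated rule, the choice between adjusted and unadjusted results is left until the data are in.

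**Working it through.** **1. The plan's own sample size.** Inputs from Sample Size: 10% versus 1%, 1:1 allocation, power 0.8. With the pooled-variance formula, n per arm = [z_a √(2·0.055·0.945) + 0.842 √(0.09 + 0.0099)]² / 0.09².
- One-sided 0.05 (equal to two-sided 0.10), z_a = 1.645: 78.3, so 79 per arm, close to the stated 80.
- One-sided 0.10, z_a = 1.282: 57.0, so 57 per arm.
- Enrolment: 160 / (1 − 0.2) = 200, as stated.

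The stated 80 with an uncorrected test therefore fits one-sided 0.05. The text says "The alpha of 0.1 is based on a one-sided hypothesis". That is a separate matter, so both levels are used below for the primary outcome.

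**2. Primary outcome.** Expected events are 80 × 0.10 + 80 × 0.01 = 8.8. Assume site rates spread evenly from 1% to 10% around 5.5%. The between-site share of variance is then 0.0010 / (0.055 × 0.945), about 0.02. A nominal one-sided 0.10 test has true size 1 − Φ(1.282/√0.98), about 0.098. Simulated power at 10% versus 1% (5 sites × 16 per arm, 20,000 runs):

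| Test | One-sided 0.05 | One-sided 0.10 |
|---|---|---|
| Uncorrected chi-square (planned) | 89% | 94% |
| Asymptotic CMH by site | 89% | 94% |
| Exact stratified | 75% | 85% |

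The 89% exceeds the 80.8% given by the normal-approximation formula at 80 per arm because that approximation is poor with so few events. The comparison between rows is what matters.

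**3. Continuous secondary outcomes.** Assumptions: two-sided 0.05 and site ICC ρ of 0.05 to 0.10; the documents give neither. Let f = 1/√(1 − ρ).
- Standard error too large by f − 1: 2.6% at 0.05, 5.4% at 0.10.
- True alpha 2[1 − Φ(1.96 f)]: 0.044 and 0.039.
- Power with the within-site SD held fixed, so that the adjusted test has 80%: Φ(2.802 − 1.96 f) = 78.5% and 76.9%. The loss is 1.5 and 3.1 points.
- Power with the total SD held fixed: unadjusted Φ(0.842 f) = 80.6% and 81.3%; adjusted Φ(2.802 f − 1.96) = 82.0% and 84.0%. The forgone gain is 1.4 and 2.7 points.

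Simulation with total SD fixed (5 sites × 40, blocks of 2, 4 and 6, 20% random loss, effect 0.446 SD, 20,000 runs) agrees. Unadjusted versus adjusted power is 80.3% versus 81.6% at ρ = 0.05 and 81.2% versus 83.9% at ρ = 0.10. At ρ = 0 it is 79.9% versus 79.6%.

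**4. Binary secondary outcomes.** Same layout, mean success about 80%, log odds ratio −1.0, two-sided 0.05, 12,000 runs, chi-square versus CMH by site:

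| Site success rates | Type I error | Power |
|---|---|---|
| All equal | 0.051 vs 0.049 | 80.9% vs 80.7% |
| 70-90% | 0.048 vs 0.051 | 77.8% vs 78.8% |
| 60-95% | 0.044 vs 0.054 | 71.4% vs 75.8% |
| 45-98% | 0.032 vs 0.051 | 60.6% vs 71.3% |

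A second simulation (5 sites × 16 per arm) with site rates of 55-97% gives type I error 0.033 versus 0.049, and power for a 15-point difference rises from 60% to 64%.

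**The case against.** The best defence is that nothing here breaks. A test whose size is below nominal still controls type I error, and the primary result barely moves.

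The secondary figures rest on inputs that the documents do not supply: between-site variance, expected success rates and alpha. The secondary hypotheses are worded as non-inferiority without a margin, whereas the figures above are for difference tests, so the plan's actual secondary power cannot be computed. Questionnaires are analysed as change from baseline, which removes stable site differences in level. All sites share one mesh, minimum graft length and suture counts, and eligibility criteria, so the widest spreads in the table are hard to credit.

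All of this stands, and it is why the point is minor. It does not remove the mismatch between design and analysis. An over-wide interval also makes non-inferiority harder to show, whatever margin is chosen.

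A reader might infer that every planned analysis excludes site. That goes too far: the regression lists no covariates, so site is unspecified there. But that regression runs only after a positive bivariate finding, so it does not supply a pre-specified site-adjusted comparison.

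**Conclusion.** The mismatch is real and its consequence is small. If sites differ, the unadjusted secondary tests are somewhat conservative. About 1 to 3 power points are forgone for continuous scores at an assumed ICC of 0.05 to 0.10. For a binary outcome the figure is about 1 point or less at site rates of 70-90% and about 4 points at 55-97%. If sites are alike, it is nil. All of this assumes two-sided 0.05.

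Two stronger readings are not supported. One is that the primary comparison is compromised: its size shifts only from 0.10 to about 0.098 under the assumed spread, and its power is within 1 point with or without site. The other is that secondary power falls below a planned level: the plan sets no secondary power, and with total SD held fixed the unadjusted power does not fall at all. What is lost is a gain that adjustment would have brought.

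**What to change.** Add to Statistical Methods:
- Composite success, symptomatic success and adverse event incidence are compared by Cochran-Mantel-Haenszel stratified by site, with a site-stratified risk difference and confidence interval.
- Models for the questionnaire scores include site as a fixed effect.
- The primary outcome keeps the planned uncorrected chi-square, or uses asymptotic CMH by site. State which.

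Do not move the primary outcome to exact stratified inference. Against the planned test it costs about 14 power points at one-sided 0.05 (89% to 75%) and 9 at one-sided 0.10 (94% to 85%). The Fisher option already in Statistical Methods costs about the same, so the text should also settle whether it can apply to the primary outcome.

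The change is SAP wording only. Site is already recorded as the letter in the subject identification number (Pre-operative/Baseline Visit), so no new data are needed. If sites turn out alike, the cost in power is a fraction of a point (80.9% versus 80.7% in the equal-site binary case).

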Participant contact information will be reviewed at each follow-up visit. All efforts will be made by site staff to ensure minimal loss to follow-up of participants and will follow a site-specific loss to follow-up plan. This plan may include efforts such as telephone follow-up, Investigator-patient counseling, visit reminder tools, patient stipends, and/or other communication methods.

Week 6 Visit (-2 weeks/+4 weeks)

The primary outcome assessed at the Week 6 visit is evidence of suture or mesh exposure at the site of the sacrocolpopexy mesh. The POP-Q examination will be performed, as well as a vaginal examination (speculum and digital) to assess for suture or mesh exposure. In addition, pain and analgesic use and adverse events will be reviewed. All efforts will be made by site staff to ensure both follow-up anatomic measurements (POP-Qs) will be conducted by a healthcare provider other than the treating surgeon to reduce bias on outcomes after the study procedure. In the event the treating surgeon is the only qualified healthcare provider at the site trained in the POP-Q, the follow-up anatomic measurements will be conducted by the treating surgeon.

The Week 6 Visit consists of the following:

- Participant Contact Form update
- Assessment of pain and analgesic use
- Review of Adverse Events (if applicable)
- POP-Q Exam
- Vaginal examination (speculum and digital) to assess for suture or mesh exposure

Month 6 Phone Call (± 4 weeks)

Patients will be contacted by phone 6 months postoperatively to review contact information, pain and analgesic use, and adverse events.

The Month 6 Call consists of the following:

- Participant Contact Form update
- Assessment of pain and analgesic use
- Review of Adverse Events (if applicable)

Year 1 Visit (± 4 weeks)

The primary outcome assessed at the Year 1 visit is evidence of suture or mesh exposure at the site of the sacrocolpopexy mesh. The POP-Q examination will be performed, as well as a vaginal examination (speculum and digital) to assess for suture or mesh exposure. In addition, pain and analgesic use and adverse events will be reviewed. Participants will also complete the PFIQ-sf7, PISQ-IR, and PFDI-sf20. All efforts will be made by site staff to ensure both follow-up anatomic measurements (POP-Qs) will be conducted by a healthcare provider other than the treating surgeon to reduce bias on outcomes after the study procedure.

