In the event the treating surgeon is the only qualified healthcare provider at the site trained in the POP-Q, the follow-up anatomic measurements will be conducted by the treating surgeon. The End of Study form will also be completed by site staff.

The Year 1 Visit consists of the following:

- Assessment of pain and analgesic use
- Review of Adverse Events (if applicable)
- PFIQ-sf7, PISQ-IR, PFDI-sf20 questionnaires
- POP-Q Exam
- Vaginal examination (speculum and digital) to assess for suture or mesh exposure
- End of Study Form

[figure not shown]
All participants who have completed the study surgery will proceed to be followed through the above-outlined study visits to Year 1 where the primary endpoint analysis will be achieved when the last per protocol subject completes this visit. All participants completing the Year 1 visit will be considered to have completed the study.

The data collection schedule of the trial is depicted in Table 1. Flow through the trial is depicted in Figure 1.

Table 1. Data Collection Schedule

	Baseline Visit	Surgery (≤ 3 mo from BL Visit)	Week 6 Visit (-2 weeks/+4 weeks)	Month 6 Call (± 4 weeks)	Year 1 Visit (± 4 weeks)
Informed Consent	X				
Medical & Surgical History Form	X				
POP-Q Exam	X		X		X
Vaginal examination (speculum and digital)			X		X
PFIQ-sf7, PISQ-IR, PFDI-sf20 questionnaires	X				X
Assessment of pain and analgesic use	X		X	X	X
Contact information update			X	X	
Surgical Procedure Form		X			
Assessment of Adverse Events		X	X	X	X
End of Study Form					X

Figure 1. Trial Flow

This protocol will adhere to the CONSORT guidelines for performing and reporting randomized controlled trials.²⁸ Women who are eligible but decline enrollment will be characterized in a manner consistent with the CONSORT requirements.

STUDY POPULATION

Inclusion Criteria

The study will include women with symptomatic uterovaginal POP, who have completed childbearing, are seeking surgical management, and are willing to proceed with placement of abdominal mesh.

1. Age ≥ 18
2. Subject must have apical with anterior or posterior vaginal prolapse with leading edge of prolapse to or beyond the hymen ($C \geq - (TVL / 2)$ AND Ba or $Bp \geq 0$ by the POP-Q)
3. Subject reports a bothersome bulge they can see or feel per PFDI-20, question 3, response of 2 or higher (i.e., responses of "somewhat", "moderately", or "quite a bit")
4. Eligible for robotic or laparoscopic sacral colpopexy

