Data will be entered by study staff at each site into a REDCap database that will be stored on a secure server by the Data Coordinating Center. Study data will be monitored by the Data Coordinating Center as outlined below under Study Monitoring and Documentation. All collected data must be entered into REDCap within 5 business days. Any queries to data entered into REDCap will be addressed by site staff within 5 business days. It is each site's responsibility to regularly check REDCap for data queries. See REDCap Data Entry Protocol for instructions on data entry and query resolution.

Each site will maintain all essential study documents in original format and source documentation that support the data collected on study participants in compliance with ICH/GCP guidelines. Documents must be retained until at least 2 years have elapsed since the formal discontinuation of the clinical investigation. Each site will take measures to ensure that these essential documents are not accidentally damaged or destroyed.

OUTCOME MEASURES

Primary Outcome Measure

The primary outcome of this trial is the incidence of vaginal mesh and suture exposure rates related to the SCP mesh for both arms of the study through 1-year after surgery. Any suture or mesh visible in the vagina that is not at the position of a midurethral sling will be considered a positive outcome. Some participants may also undergo vaginal placement of a mesh sling for stress incontinence in a more distal vaginal location. Exposure of this mesh will not be considered a positive outcome for the primary outcome.

Secondary Outcome Measures

Secondary outcomes that we will measure include a composite of objective and subjective measures, self-reported outcomes, and assessment of complications as outlined below:

1. Assessment of efficacy at 1 year of each type of suture material using the composite cure as outlined below in a-d. Participants will be considered a surgical success for this composite outcome if each of the following four criteria are met:
 - a) Anatomic success: Leading edge of the prolapse is at or above the hymen (POP-Q point Ba and Bp \leq 0) and the vaginal apex descends less than 1/3 of the total vaginal length (C $<$ - TVL/3)
 - b) Subjective success: Patient denies symptoms of vaginal bulging per PFDI-20 question 3, answering "No" or "Yes" but "Not at All" bothersome (< 2)

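### The safeguard against the operating surgeon as assessor covers only the POP-Q, not the examination that decides the primary outcome, and that outcome is defined with two different breadths

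*Combined protocol and SAP*

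**What the plan says.** **Examiner.** The Week 6 Visit and Year 1 Visit sections require a POP-Q and, as a second item, "a vaginal examination (speculum and digital) to assess for suture or mesh exposure". Each examination has its own bullet in both visit lists and its own row in Table 1. The safeguard, whose stated purpose is to reduce bias, is a best-effort request that "follow-up anatomic measurements (POP-Qs) will be conducted by a healthcare provider other than the treating surgeon". Its exception begins "In the event the treating surgeon is the only qualified healthcare provider at the site trained in the POP-Q"; in that case the surgeon takes the measurements. No section says who performs the exposure examination, and none describes masking of assessors. Under Randomization, "Randomization will be assigned using RedCAP in the operating room" means the surgeon knows the arm.

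**Breadth.** Primary Outcome Measure opens with "the incidence of vaginal mesh and suture exposure rates related to the SCP mesh". Its scoring rule follows: "Any suture or mesh visible in the vagina that is not at the position of a midurethral sling will be considered a positive outcome". Both visit sections describe the primary outcome as "evidence of suture or mesh exposure at the site of the sacrocolpopexy mesh".

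**Other sutures in the vagina.** Laparoscopic or Robotic Approach, item 1, applies to every woman: "The vaginal cuff will be closed using an absorbable suture in 1 layer". Optional Additional Procedures allows posterior and anterior colporrhaphy.

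**Where the outcome is reused.** Absence of exposure is criterion d of the composite (Secondary Outcome Measures). The overall exposure rate at the 6-week check drives the 12% rule in Criteria for Study Termination.

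**The concern.** The one explicit protection against a surgeon assessing her or his own work is attached to a measurement that feeds a secondary outcome (composite criterion a). The examination that decides the primary outcome lacks it. With so few events planned, a handful of findings recorded differently by an examiner who knows the arm could change the result.

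The two breadths raise a different problem. A visible colporrhaphy suture away from the graft is positive under the scoring rule and negative under the visit sections, so two sites could classify the same finding differently. Counting sutures unrelated to the randomised material adds events to both arms and dilutes the contrast. The same ambiguity carries into composite criterion d and the termination rule.

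**Working it through.** **Inputs from the plan (Sample Size).** Exposure 10% with permanent and 1% with absorbable suture; 80 evaluable women per arm; power 0.8; one-sided alpha 0.1; uncorrected chi-square; 200 enrolled. Expected events: 80 × 0.10 = 8 and 80 × 0.01 = 0.8.

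**The plan's own figure.** The pooled-variance formula is n = [z(α)√(2p̄(1−p̄)) + z(β)√(p1(1−p1)+p2(1−p2))]² / (p1−p2)². With p̄ = 0.055 and a difference of 0.09 it gives 57.0 per arm at one-sided 0.1 and 78.3 (79) at one-sided 0.05. The stated 80 therefore matches one-sided 0.05, not the stated level. That is a separate matter; the results below use the stated level unless noted.

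**Method.** Exact enumeration of two independent binomials, 80 per arm, rejecting when z > 1.282 in favour of absorbable suture. The documents give no value for q or m below; both are assumptions shown over a range.

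**Check 1: breadth.** Let q be the share of women in both arms with a visible non-study suture. The arm rates become 1 − (1−p)(1−q).

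| q | Permanent | Absorbable | Difference | Power |
|---|---|---|---|---|
| 0% | 10.0% | 1.00% | 9.00 points | 94% |
| 1% | 10.9% | 1.99% | 8.91 | 89% |
| 2% | 11.8% | 2.98% | 8.82 | 84% |
| 3% | 12.7% | 3.97% | 8.73 | 80% |
| 5% | 14.5% | 5.95% | 8.55 | 72% |

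The difference barely moves; the loss comes from added noise. Statistical Methods sends small outputs to Fisher's exact test. With that test at one-sided 0.1, power is 84.8, 78.2, 72.7, 68.0 and 60.5%.

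**Check 2: termination rule.** Half of 200 is 100 women, so more than 12% means at least 13 exposures. Take the average of the two arm rates, and suppose that between half and all of the 1-year exposures are present at 6 weeks. The chance of crossing is at most 0.3% at q = 0, 0.4–7% at q = 3% and 4–22% at q = 5%.

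**Check 3: examiner.** Suppose true exposure is 8% in both arms, the 1-year rate quoted in the Background for permanent suture, and that a share m of exposures goes unrecorded in one arm only. The chance of wrongly concluding that absorbable suture is better is:

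| m | Missed in absorbable arm | Missed in permanent arm |
|---|---|---|
| 0% | 10.8% | 10.8% |
| 10% | 14.8% | 7.7% |
| 20% | 19.9% | 5.3% |
| 30% | 26.3% | 3.4% |

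The error can run either way, and nothing in the documents fixes its direction.

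**The case against.** **Intent on the examiner.** The safeguard sentence sits in the same paragraph as the exposure examination and speaks of bias on outcomes generally. One provider doing both examinations is a natural reading. That stands: this is a gap in the wording. A reader might infer that surgeons will score the primary outcome, or that the trial is tilted towards absorbable suture. The documents support neither. The text permits a surgeon to examine but does not assign the task, and the bias could favour either arm. The outcome is also a visible object, and the Background notes that the blue mesh may help detection.

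**Scope of the rule.** The opening sentence of Primary Outcome Measure can be read as limiting the rule that follows, and the documents do not place the cuff away from the graft, so the wordings may agree on cuff sutures. This also stands. The clear conflict is over a colporrhaphy suture away from the graft.

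**Imbalance.** A reader might infer that the broad rule biases the comparison. It does not follow. Non-study sutures should be balanced by randomisation. Posterior repair is tied to a measured Bp threshold; anterior repair has a discretionary clause, but nothing suggests that suture type changes how often it is done. The effect is dilution.

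**Power.** On the plan's stated test and level, 80% power survives to about q = 3%, and no figure in the documents supports any q above zero. Sample Size also does not say whether the source rates already include such sutures. That limits the weight of Check 1.

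**Unseen material.** The follow-up forms listed under Site Documentation and the REDCap Data Entry Protocol were not supplied and may already record location and type.

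**Conclusion.** Both gaps are in the text and are worth closing; this is a cheap improvement. The examiner gap is the only source of possible directional bias. Under the assumptions of Check 3, the false-positive chance moves from 11% up to 15, 20 or 26%, or down to 8, 5 or 3%, depending on which arm is under-recorded. The breadth gap dilutes: power falls from 94% to 89, 84, 80 and 72% at q = 1, 2, 3 and 5%.

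It would be tempting to present that whole loss as the gain from a fix. It is not. The cuff suture is the only non-study suture every woman has, and it stays counted under the definition proposed below, so only the part due to colporrhaphy sutures away from the graft is removed. All of these sizes rest on assumed q and m.

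**What to change.** 1. **Examiner.** In both visit sections, extend the safeguard to cover the POP-Q and the vaginal examination for suture or mesh exposure, and record who examined. Do not extend the POP-Q-training fallback to the exposure examination, and do not require one provider for both. Either step could hand the primary outcome to the surgeon at a site where only the surgeon is POP-Q trained. There, another available qualified provider should still do the exposure examination.
2. **Definition.** Reconcile Primary Outcome Measure with the visit sections in one definition applied alike in both arms. Count mesh or suture at the sacrocolpopexy graft site, including the cuff line. Do not count items at a sling position or on a colporrhaphy line clearly away from the graft. Do not classify by suture type: dropping absorbable cuff-line sutures would remove PDS exposures but no permanent ones. Use the same definition for composite criterion d and the termination rule, and record the type and location of each visible item.
3. **Sensitivity analyses.** Report the result under the literal any-visible-item rule, and the result without suture-only cuff-line findings. The gap between the latter and the primary result is an upper bound on cuff-suture dilution, not an estimate of it.

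**Cost.** Wording in five places (the Week 6 and Year 1 sections, Primary Outcome Measure, criterion d, the termination rule) and one or two form items, unless the forms already hold them. No new staff are needed where a provider other than the surgeon already does the POP-Q. Two downsides remain: slightly more judgement near repair lines, and incomplete masking, because a visible suture may reveal the arm.
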